3.7.2.3 Adverse Events of Special Interest

The TEAEs of bleeding based on the Haemorrhages (SMQ) Export from MedDRA version 20.1 will be summarized by SOC and PT and by severity in on-treatment and on-study period respectively.

The TEAEs of bleeding in presence or absence of concomitant antithrombotic medication (ATC3 Text: Antithrombotic agents) will be summarized by SOC and PT in on-treatment period. The TEAEs of bleeding in presence or absence of concomitant antithrombotic medication will be listed as well.

An additional table summarizing treatment-emergent bleeding AEs on-treatment by SOC and PT within cohort will be presented.

3.7.3 Vital Signs Measurements

Vital signs include weight, BMI, body temperature, heart rate, respiratory rate, systolic and diastolic blood pressure. Vital signs will be summarized using the descriptive statistics (n, mean, standard error, standard deviation, median, P25, P75, minimum, maximum, and mean 95% CI) for observed values, change from baseline and percent change from baseline at each nominal study visit. Scheduled visits will be used for summary table. A listing of vital signs with scheduled and unscheduled visits will also be provided.

3.7.4 Laboratory Measurements

The following is the list of lab analytes that will be collected throughout the study:

- Chemistry: sodium, potassium, chloride, bicarbonate, total protein, albumin, calcium, magnesium, phosphorus, glucose, blood urea nitrogen (BUN), creatinine, glomerular filtration rate, uric acid, total bilirubin, direct bilirubin, indirect bilirubin, alanine aminotransferase (ALT), aspartate aminotransferase (AST), alkaline phosphatase (ALP), creatine kinase, GGT, Cystatin-C
- Hematology: red blood cells, hemoglobin, hematocrit, mean corpuscular hemoglobin (MCH), mean corpuscular volume (MCV), mean corpuscular hemoglobin concentration (MCHC), platelets, white blood cells (WBCs), and WBC differential (percentage and absolute count), neutrophils, eosinophils, basophils, lymphocytes, and monocytes
- Coagulation: activated partial thromboplastin time (aPTT), prothrombin time (PT), and international normalized ratio (INR)
- Inflammatory Panel: C-reactive protein measured by high sensitivity assay (hsCRP)
- Test Performed at Screening Only: Hepatitis B surface antigen, Hepatitis C antibody, HIV antibody, follicle-stimulating hormone (FSH) (women only), serum beta-subunit of human chorionic gonadotropin (β hCG) (women only), thyroid stimulating hormone (TSH), free T4. The screening test data will only be displayed in patient listings
- Urinalysis: color, appearance, specific gravity, pH, protein, red blood cell, ketones, glucose, urobilinogen, bilirubin, leukocytes esterase, nitrate. For expanded urinalysis at certain visits,

additional measurements will be performed including: microscopic examination, urine protein/creatinine ratio (UPCR), urine albumin/creatinine ratio (UACR).

- Renal Urine Biomarkers: NGAL, NAG, KIM-1, Cystatin-C
- Other assessments (glycemic control): plasma insulin, fasting plasma glucose, homeostatic model assessment of insulin resistance (HOMA-IR) as provided in the central laboratory data, fructosamine, glycated albumin, and glycated hemoglobin (HbA1c)

Missing WBC differential absolute counts and percentages will be derived: If WBC differential absolute counts are missing, and percentages are available, then absolute counts will be calculated by multiplying the percentage by total WBC count. Conversely, if absolute count is available, and percentage is missing, then percentage will be calculated by dividing absolute count by the total WBC count. If neutrophil counts and percentages are missing, and segmented neutrophil and band neutrophil results are available, then neutrophils will be calculated by adding segmented neutrophils and band neutrophils.

Quantitative laboratory measurements reported as ‘< X’, i.e. below the lower limit of quantification (BLQ), or ‘> X’, i.e. above the upper limit of quantification (ULQ), i.e. outside the limit of quantification, will be converted to X (or limit of quantification) for the purpose of quantitative summaries. If urine albumin/creatinine ratio (UACR) or urine protein/creatinine ratio (UPCR) is ‘Cannot calc’ indicating urine albumin or urine protein in the below quantification range, UACR and UPCR will be calculated as the ratio of urine albumin or urine protein to urine creatinine after converting urine albumin or urine protein to the limit of quantification.

Estimated Glomerular Filtration Rate (eGFR) is based on the Chronic Kidney Disease-Epidemiological Collaboration (CKD-EPI) Equation and is provided as a parameter in the central laboratory data.

Chemistry, hematology, inflammatory panel, coagulation, other assessments, renal biomarkers, and quantitative urinalysis (observed value, absolute and percent change from baseline) will be summarized using descriptive statistics (n, mean, standard error, standard deviation, median, P25, P75, minimum, and maximum, mean 95% CI) by scheduled nominal visit. HOMA-IR and plasma insulin will be summarized only in patients not treated with insulins or insulin analogues. Qualitative urinalysis will be summarized using counts and percentages by scheduled nominal visit. Lab summary table except for platelet count will be based on the scheduled visits in central lab data only with the results in original unit. The summary table of platelet count will be based on the scheduled visits in central and separately in local lab data with the results in original unit.

All laboratory test results will be listed separately for local and central labs at scheduled and unscheduled visits with results in original unit.

A confirmed laboratory value is based on consecutive lab values performed on a different day to, but within 7 days (no matter central lab data or local lab data). If consecutive value is same or worse, then the initial value is confirmed. If the consecutive value is better, then the initial value is confirmed using consecutive value. If there is no retest within 7 days, then the initial value is presumed

confirmed. If there are multiple results on the same day (no matter central lab data or local lab data), then the worst value will be utilized in the analysis.

The following lab results will be graded based on Toxicity Grading Scale for Healthy Adult and Adolescent Volunteers Enrolled in Preventive Vaccine Clinical Trials (September 2007). Number and proportion of patients with shift from baseline to worst post-baseline values by toxicity grade will be tabulated for on-treatment and on-study periods. Post-baseline lab results are defined as any assessment taken after the first dose no matter central lab or local lab data. If a patient has no baseline value but has a post-baseline value, then the baseline assessment will be labeled as “unknown”. Likewise, if a patient has a baseline value but has no post-baseline value, then the worst value will be labeled as “unknown”. Shift tables for eGFR, ALT, AST and total bilirubin will be provided using original and confirmed values.

- Hemoglobin: shift from Baseline to minimum post-baseline value
- WBCs: shift from Baseline to minimum post-baseline value
- Platelets: shift from Baseline to minimum post-baseline value
- BUN: shift from Baseline to maximum post baseline value
- Creatinine: shift from Baseline to maximum post-baseline value
- eGFR: shift from Baseline to minimum post-baseline value
- Proteinuria: shift from Baseline to worst post-baseline value
- ALT: shift from Baseline to maximum post-baseline value
- AST: shift from Baseline to maximum post-baseline value
- Alkaline phosphatase: shift from Baseline to maximum post-baseline value
- Total bilirubin: shift from Baseline to maximum post-baseline value

eGFR will be graded using the following criteria:

- $\geq 90 \text{ mL/min}/1.73\text{m}^2$
- $\geq 60 \text{ mL/min}/1.73\text{m}^2$ to $< 90 \text{ mL/min}/1.73\text{m}^2$
- $\geq 30 \text{ mL/min}/1.73\text{m}^2$ to $< 60 \text{ mL/min}/1.73\text{m}^2$
- $\geq 15 \text{ mL/min}/1.73\text{m}^2$ to $< 30 \text{ mL/min}/1.73\text{m}^2$
- $< 15 \text{ mL/min}/1.73\text{m}^2$

The number and percent of patients who stopped treatment because they met a protocol-defined safety monitoring rule(s) and stopping rule(s) (see Protocol Section 8.6 for details) will be tabulated by treatment group. A listing will be provided for patients who met protocol-defined safety monitoring rules and for patients who terminated treatment due to a protocol-defined stopping rule as well.

Additional investigation of abnormalities in liver chemistry, platelet counts, and renal functions will be performed for on-treatment and on-study periods as below.

Abnormalities in liver chemistry: The number and percent of patients falling in each of the following categories (using available central and local laboratory assessments) will be tabulated based on worst post-baseline assessments by treatment group and for pooled ISIS 678354.

- The higher of ALT > 3 x upper limit of normality (ULN) or ALT > 2 x Baseline
- ALT/AST > 3 x ULN
- ALT/AST > 5 x ULN
- ALT/AST > 8 x ULN
- ALT > 3 x ULN - ≤ 5 x ULN
- ALT > 5 x ULN - ≤ 8 x ULN
- Total bilirubin > 2 x ULN
- ALP > 2 x ULN and (baseline ALP < 2 x ULN or baseline ALP missing)

The number and percent of patients falling in each of the following categories based on confirmed worst post-baseline assessments will be tabulated by treatment group and for pooled ISIS 678354.

- ALT/AST > 8 x ULN, which is confirmed
- ALT/AST > 5 x ULN, which is confirmed and persist for at least 2 weeks
- ALT/AST > 3 x ULN (or the greater of 2 x Baseline value or 3 x ULN if the Baseline value was > ULN), which is confirmed and either:
 - Total bilirubin > 2 x ULN, or
 - INR > 1.5, or
 - Temporal association with symptoms of fatigue, nausea, vomiting, right upper quadrant pain or tenderness (PT: abdominal pain or abdominal pain upper), fever, rash, or eosinophilia (PT: Eosinophilia and the corresponding lab value >ULN within the interval of associated Eosinophilia start and end date); and where temporal will be defined as the report date of the confirmed laboratory parameter occurring within the interval of the associated adverse event start and stop dates

For patients having confirmed 3-fold or greater elevations above the ULN for ALT or AST, a listing of all ALT, AST, total bilirubin, INR, and alkaline phosphatase records will be provided.

Abnormalities of platelet counts: The number and percentage of patients falling in each of the following categories (using available central and local laboratory assessments) based on worst post-baseline assessments will be provided:

- Any 2 occurrences of platelet count < 140,000 cells/mm³
- Any single occurrence of platelet count < 100,000 cells/mm³
- Any 2 occurrences of platelet count < 140,000 cells/mm³ or any single occurrence of value < 100,000 cells/mm³

The nadir platelet count will be summarized by following categories:

- Decrease \geq 30% from baseline
- Decrease \geq 50% from baseline
- 100,000 cells/mm³ to < 140,000 cells/mm³
- 75,000 cells/mm³ to < 100,000 cells/mm³
- 50,000 cells/mm³ to < 75,000 cells/mm³
- 25,000 cells/mm³ to < 50,000 cells/mm³
- 0 to < 25,000 cells/mm³

All categories of abnormalities in platelet count will be summarized based on confirmed values for on-study period as well.

Abnormalities of renal function: The number and percentage of patients falling in each of the following categories (using available central and local laboratory assessments) based on confirmed worst post-baseline assessments will be provided:

- eGFR by CKD-EPI $>$ 25% decrease from baseline
- UACR $>$ 250 mg/g
- UPCR $>$ 0.5 g/g
- Serum creatinine increase of $>$ 0.3 mg/dL from baseline

3.7.5 12-Lead Electrocardiogram

ECGs will be performed in triplicate at the visits indicated in the Protocol Appendix A. Patients in PK Subgroup will have additional ECG conducted during the treatment period. Patients determined to have a pacemaker rhythm will be excluded from summary tables.

The ECG data include ventricular rate, PR interval, QRS duration, QT and corrected QT intervals. For the continuous variables, the average of measurements at a given visit will be used for analysis. For the continuous variables above, descriptive statistics (n, mean, standard error, standard deviation, median, P25, P75, minimum, maximum, and mean 95% CI) of the observed values, as well as the change from baseline to each nominal study visit, will be presented by treatment group and for pooled placebo in summary tables. The summary table will be presented in SS and in PK Subgroup separately. Scheduled visits will be used for all summary tables.

The number and percent of patients who have the following reported events will be tabulated by treatment group and for pooled ISIS 678354.

- Absolute QT/QTcF/QTcB $>$ 450 msec
- Absolute QT/QTcF/QTcB $>$ 480 msec

- Absolute QT/QTcF/QTcB >500 msec
- Increase from baseline in QT/QTcF/QTcB >30 msec
- Increase from baseline in QT/QTcF/QTcB >60 msec
- Increase from baseline in PR \geq 50% (if absolute baseline <200 msec)
- Increase from baseline in PR \geq 25% (if absolute baseline >200 msec)
- Increase from baseline in QRS \geq 50% (if absolute baseline <100 msec)
- Increase from baseline in QRS \geq 25% (if absolute baseline >100 msec)

QTcB (msec) = QT (msec) / (RR)^{1/2}; if RR is missing, use QT (msec) * (HR(bpm)/60)^{1/2}

QTcF (msec) = QT (msec) / (RR)^{1/3}; if RR is missing, use QT (msec) * (HR(bpm)/60)^{1/3}

All the ECG data with scheduled and unscheduled visits will be listed.

An exploratory exposure-response analysis will be performed in PK-ECG Set to evaluate the relationship between QTcF and plasma concentration of ISIS 678354. The relationship between ISIS 678354 concentration and change from baseline QTcF (Δ QTcF) and placebo-corrected change from baseline QTcF ($\Delta\Delta$ QTcF) will be investigated using a linear mixed-effects modeling approach on time-matched ECG and ISIS 678354 concentration data.

Δ QTcF or $\Delta\Delta$ QTcF = $\alpha + \beta_1 \times [\text{ISIS 678354 concentration}] + \beta_2 \times [\text{baseline QTcF}] + \gamma \times [\text{patient effect}]$

$\Delta\Delta$ QTcF = (Δ QTcF for ISIS 678354 treated patient) – (mean of Δ QTcF for pooled placebo group).

Matching of ECG and ISIS 678354 concentration (PK) data will be based on the following algorithm, in the sequence provided:

1. Time of ECG and PK must be within 60 minutes (\pm 60 minutes) of each other.
2. If there are multiple records within the 60 minutes range, the closest match will be chosen.
3. If there is more than one closest match identified in the previous step, the recorded pair with the ECG time point after the PK time point will be chosen.

Plots of Δ QTcF or $\Delta\Delta$ QTcF versus ISIS 678354 concentration including all patients in PK-ECG Set will be generated.

3.8 *Interim Analysis*

There is no interim analysis planned for the study.

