3.2.2 Reporting Conventions

Efficacy results will be summarized under the treatment to which patients were randomized. Safety and PK results will be summarized under the treatment which patients actually received. Should there be any cases after unblinding in which a patient received treatment other than what the patient was

randomized to, such cases will be discussed in the study report and noted in footnotes where applicable.

All tables will present the population frequencies in each treatment group and/or subgroup (where appropriate) and will indicate the number of patients with non-missing data and the denominators for percentages.

Descriptive summary statistics including n, mean, median, standard error, standard deviation SD, interquartile range (25th percentile, 75th percentile), range (minimum, maximum), mean 95% confidence interval (CI) for continuous variables, and counts and percentages for categorical variables, will be used to summarize data by treatment group. Summaries of PK concentrations and parameters will also include coefficient of variation (CV%), geometric mean, and geometric CV%. Where appropriate, p-values will be reported. All statistical tests will be conducted using 2-sided tests with 5% Type I error rates unless otherwise stated.

Except summaries for PK parameters, precision for displays will use the following conventions. Means, percentiles (e.g., median, 25th and 75th percentile), least squares means, difference in least squares means will be displayed to one more decimal place than measured values. Standard deviations and standard errors will be displayed to two more decimal places than measured values. The minimum, maximum and confidence intervals will be displayed using the same number of decimal places as the recorded values. All raw values presented in listings will be displayed to the measured precision. Percentages will be displayed to one decimal place. For PK concentrations and parameters, mean, standard deviation, standard error, geometric mean, median, minimum, and maximum values will be presented to 3 significant digits and CV% and geometric CV% will be presented to one decimal place. p-value will be displayed to 4 decimal places. p-value less than 0.0001 will be presented as “<0.0001”. p-value greater than 0.9999 will be displayed as “>0.9999”. Confidence intervals will be presented using a comma separator rather than a dash.

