3.2.4 Baseline and Endpoint Definition

For platelet count data, central and local lab will be used in baseline derivation. For other lab data, only central lab will be used in baseline derivation.

Baseline for lipid panel is defined as the average of Day 1 fasting pre-dose assessment and the last non-missing fasting measurement prior to Day 1 pre-dose assessment. If 1 of the 2 measurements is missing, then the other measurement will be assigned as the baseline value. If both are missing, then the baseline will be set as missing. Note that if on Day 1, there are multiple pre-dose assessments, then the last assessment with non-missing value will be used as the Day 1 pre-dose assessment.

Baseline for platelet is defined as the average of all assessments prior to the first dose of Study Drug.

Baseline for ECG is the average of the triplicate taken on Day 1 pre-dose for ECG summary over time and abnormal ECG parameters tables. If only one or two assessments are available, the single assessment or average of the two assessments will be used. If ECG results on Day 1 pre-dose is missing, results at screening visit will be used as baseline.

Baseline for other measurements is defined as the last non-missing assessment prior to the first dose of Study Drug.

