3.3.2 Primary Efficacy Analysis

The primary efficacy analysis for the primary endpoint will be the pairwise comparison of percent change from baseline to the primary analysis time point in fasting triglycerides between ISIS 678354 treated groups and pooled placebo group in the FAS.

The percent change from baseline in triglycerides will be analyzed using an ANCOVA model with treatment group as a fixed factor and log-transformed baseline triglycerides as a covariate. The ANCOVA model will use $\log(Y/X)$ as dependent variable, where Y is the post-baseline value of triglycerides and X is the baseline value of the triglyceride. The model will provide an estimate of the log ratio, which will then be converted back to the original ratio scale. The percent change from baseline will then be estimated based on the estimated ratio. Patients with missing primary endpoint will have their fasting triglyceride value imputed using the multiple imputation method described below.

Missing data for the primary efficacy endpoint will be handled by a multiple imputation model that contains the following variables: log-transformed baseline fasting triglyceride value, log-transformed fasting post-baseline triglyceride values, stratified by treatment ([Schafer 1997](#); [Schafer 1999](#)). Imputation of missing data will be conducted under a working assumption of missing at random (MAR), meaning that the propensity for a data point to be missing is not related to the missing data, but it is related to some of the observed data.

The imputations will be performed for post-baseline visits. The Markov Chain Monte Carlo (MCMC) method will be used under the multivariate normality assumption to impute the missing primary endpoint by treatment group (ISIS 678354 treatment group or pooled placebo treatment group). In order to be compliant with the normality assumption, baseline and post-baseline triglyceride data will be log-transformed prior to the imputation process and will be reverted when creating the imputed dataset. The MCMC method will impute 100 datasets in order to estimate the treatment effect, where the median value across the imputed datasets will be used for patients with missing endpoint.

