3.5 Exploratory Efficacy Analyses

All analyses of exploratory endpoints will be performed on the FAS. Percent change from baseline at the primary analysis time point in fasting Lp(a), remnant cholesterol, and ANGPTL3 as log-transformed ratio of post-baseline to baseline value will be compared between each ISIS 678354 group and pooled placebo group using an ANCOVA model with log-transformed baseline as covariate. Summary statistics including observed value, change and percent change from baseline by analysis visit will also be performed.

Table 5 outlines the analysis methods used in each efficacy analysis.

Table 5 Summary of Analysis Methods in Efficacy Analyses

Endpoint	Analysis Type	Log-Transformed Data	MCMC imputation	Population	Model
Primary Endpoint	Primary Analysis	Yes	Yes, assume MAR	FAS	ANCOVA
	Sensitivity Analysis 1	Yes	Yes, assume MAR	PPS	ANCOVA
	Sensitivity Analysis 2	Yes	Yes, assume MAR	FAS	non-parametric Wilcoxon Rank Sum test
	Sensitivity Analysis 3	Yes	Yes, assume MAR	PPS	non-parametric Wilcoxon Rank Sum test
	Sensitivity Analysis 4	Yes	Yes, Placebo: assume MAR. ISIS 678354: missing before discontinuation, assume MAR; missing after discontinuation assume CIR	FAS	ANCOVA
	Sensitivity Analysis 5	Yes	No	FAS	ANCOVA
	Sensitivity Analysis 6	Yes	No	FAS	MMRM
	Subgroup Analysis	Yes	Yes	FAS	ANCOVA
Secondary Endpoints	Secondary Analysis	Yes	Yes for triglycerides; No for other endpoints	FAS and PPS	ANCOVA
Exploratory Endpoint	Exploratory Analyses	Yes	No	FAS	ANCOVA

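### For the four urine kidney-injury markers, the planned mean percent change is expected to exceed zero when nothing has changed; add a geometric mean ratio to baseline with its 95% CI

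*Combined protocol and SAP*

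**What the plan says.** SAP 3.7.4 lists the analytes as "Renal Urine Biomarkers: NGAL, NAG, KIM-1, Cystatin-C" and states that "renal biomarkers, and quantitative urinalysis (observed value, absolute and percent change from baseline) will be summarized using descriptive statistics". The statistics are n, mean, standard error, standard deviation, median, quartiles, minimum, maximum and a 95% CI for the mean, at each scheduled nominal visit. SAP 3.2.4 sets the baseline: "Baseline for other measurements is defined as the last non-missing assessment prior to the first dose of Study Drug". The two-value average in Protocol 8.5 and 8.6 serves the monitoring and stopping rules, not these tables. A result outside the quantification range "will be converted to X (or limit of quantification) for the purpose of quantitative summaries".

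Elsewhere the SAP does work on a ratio scale. For the primary triglyceride ANCOVA, "The model will provide an estimate of the log ratio, which will then be converted back to the original ratio scale". The exploratory lipids are analysed "as log-transformed ratio of post-baseline to baseline value will be compared between each ISIS 678354 group" and pooled placebo. In SAP 3.2.2 (Reporting Conventions), "Summaries of PK concentrations and parameters will also include coefficient of variation (CV%), geometric mean, and geometric CV"%. No geometric or log-ratio summary is planned for the urine markers.

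SAP 3.7.4 also has a categorical renal table ("Abnormalities of renal function: The number and percentage of patients falling in each of the following categories"), but its categories are eGFR, UACR, UPCR and serum creatinine. The four urine markers are not in it, nor in the shift tables. Apart from listings, the by-visit table is their only planned output.

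**The concern.** Percent change divides a noisy value by another noisy value. A baseline that happens to be low produces a large positive percentage, while an equally low follow-up value cannot produce a fall beyond 100%. The arithmetic mean of such ratios therefore sits above no change even when each patient's underlying level is constant. The CI is centred on that shifted mean, and it is the only interval the plan gives for these markers on a relative scale.

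Protocol 8.5.2 describes these as markers of acute renal injury. A row showing a mean rise with a CI above zero could be read as a renal signal in that regimen when there is none.

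**Working it through.** The plan states no figure on this point, so there is none to reproduce.

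**Inputs from the documents.** Each cohort has 25 patients randomised 4:1 (Protocol Synopsis, Treatment Groups). That gives 25 × 4/5 = 20 per active group and 4 × 5 = 20 on pooled placebo. There is one baseline value (SAP 3.2.4).

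**Assumptions not in the documents.** Values are log-normal and independent around a constant patient level. The within-patient CV is 10% to 100%. One visit is considered at a time.

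**Offset.** Let X be baseline, Y the visit value and s² = ln(1 + CV²). With no true change, log(Y/X) has mean 0 and variance 2s². Hence E[Y/X] = exp(s²) = 1 + CV², and the expected mean percent change is 100 × CV². At CV 30%, for example, 100 × 0.09 = +9%.

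The direction does not depend on log-normality. For any exchangeable positive X and Y, E[Y/X] is at least 1 while log(Y/X) is centred on 0. Only the size depends on the distribution.

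**Simulation of the planned t interval** (no true change, n = 20, 100,000 arms per CV; nominal 2.5% on each side):

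| Assumed CV | Expected mean % change | CI wholly above 0 | CI wholly below 0 |
|---|---|---|---|
| 10% | +1% | 3.7% | 1.6% |
| 20% | +4% | 5.4% | 1.1% |
| 30% | +9% | 7.5% | 0.8% |
| 50% | +25% | 12.3% | 0.4% |
| 75% | +56% | 17.2% | 0.2% |
| 100% | +100% | 20.1% | 0.1% |

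A separate run of 40,000 arms gave 5.5%, 7.7%, 12.0% and 19.9% above zero at CV 20%, 30%, 50% and 100%.

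**Other summaries under the same conditions.**

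- Geometric mean ratio: centred on no change at every CV (simulated −0.2% to +0.1%), with its CI wholly above no change in 2.4% to 2.6% of arms.
- Absolute change (planned): CI wholly above zero in 1.4% to 2.5% of arms.
- Median percent change (planned): the typical arm median is within 0.5 points of 0. Averaged over arms it is +0.4%, +0.7%, +1.6% and +5.7% at CV 20%, 30%, 50% and 100%.
- Active minus placebo difference in mean percent change: −0.25 to +0.21 points, because both arms carry the same offset.

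**Effect of the quantification limit.** If 30% of values (an assumption) are set to the limit, the offset falls to about +2%, +5%, +13% and +49% at CV 20%, 30%, 50% and 100%.

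**The case against.** The strongest reply is that the same sentence of the SAP already supplies the remedy. It lists the median and quartiles of percent change, and the observed value and absolute change. The Protocol Synopsis says safety results will be compared with placebo, which has the same offset. To be misled, a reader must take one arm's mean and ignore the median, the absolute change and the placebo column. This stands, and it is why the point is minor. What it leaves is that the only relative-scale interval is off-centre.

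A reader might also infer that the SAP handles these markers worse than lipids. The documents do not support that. Log ratios appear only in the lipid ANCOVA models. The descriptive lipid tables in SAP 3.3.2, 3.4 and 3.5 use raw percent change, and SAP 3.3.2 plots its mean over time.

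Nor can it be argued that the ratio would detect a drug effect more often. Such a gain needs an interval for active against placebo. The plan has none for these markers, and the change proposed here adds none.

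Two further objections hold in part. The size rests on a CV that nobody can read from the documents, and at a low CV little is gained. The arithmetic also applies to any variable analyte in the same sentence, such as hsCRP, UACR or UPCR, and nothing in the documents shows that these four vary more. They are singled out because of their stated role as injury markers and the lack of any other table for them.

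**Conclusion.** The point holds for one statistic: the within-arm arithmetic mean percent change and its CI. Its expected offset with no true change is about CV squared. That is +1% to +100% over the assumed CV range, and less if many values sit at the quantification limit. The cancellation against placebo assumes equal within-patient variability in the arms.

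A reader might go further and infer a false renal difference between drug and placebo, or a risk to patient management. Neither follows. The comparison with placebo is not shifted when there is no effect. The renal alerts in Protocol 8.5.2, the stopping rules in 8.6.2 and the SAP's abnormality categories use eGFR, UACR, UPCR and serum creatinine, not these markers. No hypothesis test uses them. Severity is minor.

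**What to change.** In SAP 3.7.4, keep every planned statistic. Protocol 10.6.2.2 calls for safety laboratory variables to be shown as change and percent change, so the mean percent change should not be deleted. Add one sentence for urine NGAL, NAG, KIM-1 and cystatin-C: at each scheduled visit, for each treatment group and pooled placebo, report the geometric mean ratio to baseline with its 95% CI, obtained as the mean of log(Y/X) with its t interval, exponentiated. State that relative change in these markers will be described from this ratio rather than from the mean percent change.

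The cost is one extra row in a descriptive table, from data already collected. Values below the quantification limit are already replaced by the limit, so the logarithm exists. There are two downsides. These four analytes would carry a row that the other laboratory tests lack, and if many values sit at the limit the ratio is pulled towards 1, just as percent change is pulled towards 0.
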